**Non-hematological toxicity:**

- $\geq$  Grade 3 nausea, vomiting or diarrhea persisting more than 3 days despite optimal medical support
- $\geq$  Grade 3 fatigue persisting  $> 7$  days
- Any other  $\geq$  Grade 3 adverse event
- Failure to recover from AMG 397 related toxicities to grade  $\leq 1$  or baseline severity after delaying next cycle up to 14 days

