#### **Dosage Adjustments**

The subject should continue on the same dose of AMG 397 throughout the study unless the following events occur:

- For subjects experiencing an adverse event meeting the DLT definition or intolerable related adverse events BUT showing evidence of response, there will be an option to reduce the dose to the immediate next lower dose level shown to be safe and tolerable in the dose escalation part of the study.
- AMG 397 can be resumed once the adverse events recover to baseline or Grade 1 and the reintroduction of AMG 397 is deemed safe by the Investigator, Amgen's Medical Monitor, and Global Safety Officer.

**NOTE:** Subjects must be informed of the risk of continuing on therapy. Each subject is only allowed a single dose reduction.

Subjects should not be re-challenged with AMG 397 if the following AMG 397-related adverse events occur:

- Any life-threatening adverse events
- DILI (Drug Induced Liver Injury) meeting Hy's law
- Persistent grade 3 adverse events that do not recover to baseline or Grade 1 within 4 weeks of last dose
- Any treatment-related adverse event meeting DLT-criteria that recurs

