**For MM and NHL subjects only:**

A DLT is defined as a treatment-related AE(s), that occur during the DLT-observation period (see [Section 6.2.1.2](#)) including any:

- $\geq$  Grade 3 non-hematological AE's **EXCEPT**:
  - $\geq$  Grade 3 fatigue if  $<7$  days
  - Grade 3 nausea, vomiting and/or diarrhea if  $< 3$  days and controlled with medical management
  - Laboratory parameters of grade  $\geq 3$  that improve with medical management to grade  $\leq 2$  within 3 days
- $\geq$  Grade 4 hematologic AE's AND:
  - $\geq$  Grade 3 neutropenia with fever
  - $\geq$  Grade 3 thrombocytopenia with Grade  $\geq 2$  hemorrhage
  - $\geq$  Grade 3 anemia with symptoms requiring intervention (eg, transfusion)

**NOTE:**  $\geq$  Grade 4 neutropenia must be lasting  $> 7$  days

- Any grade 5 AE that is not clearly due to disease progression

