**For AML subjects only:**

Due to the nature of AML, hematologic adverse events will not be considered DLTs. However, prolonged pancytopenia in the presence of a hypocellular bone marrow (ie, cellularity 5% or less without evidence of leukemia) that lasts longer than 42 days will be considered dose-limiting myelosuppression.

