#### 10.4 Adaptive Design

A 2-parameter Bayesian Logistic Regression Model (BLRM) is used to guide dose escalation. The MTD target Toxicity Probability Interval (TPI) for DLT is (0.20, 0.33] and TPIs of (0.33, 0.60] and (0.60, 1.00] are defined as excessive and unacceptable, respectively. The design seeks to identify a dose most likely to have a DLT rate in the target TPI, but with overdose control that limits the possibility the dose has an excessive or unacceptable DLT rate (Babb et al, 1998). The overdose control limit is defined as less than a 0.40 probability of an excessive or unacceptable TPI. Based on accumulating safety data, the DLRT may implement an overdose control limit of less than a 0.25 probability of an excessive or unacceptable TPI. The probability of a DLT at dose level  $d_i$  is assumed to follow a Bernoulli distribution with probability  $p_i$  where the logit of  $p_i$  increases linearly with the log of the standardized dose in the following 2-parameter logistic model:

$$\log [p_i / (1-p_i)] = \text{logit}(p_i) = \log[a] + \exp(\log[b]) \log (d_i / d_{\text{ref}})$$

where  $a$  and  $b$  are random variables and  $d_{\text{ref}}$  is 1 of the planned dose selected as the reference dose.

A bi-variate normal prior distribution (Neuenschwander et al, 2008) is used for  $\theta = (\log a, \log b)$  where the probability that the true DLT rate is  $\leq 0.40$  at the lowest planned dose of 80 mg is 0.90 and the probability the true DLT rate is  $\leq 0.05$  at the reference dose of 640 mg is 0.05. These values are selected such that  $p_i$  is 0.05 for the starting dose and 0.25 for the reference dose. Model sensitivity to the prior will also be investigated and in particular the BLRM will be examined using a prior having a lower reference dose (eg, 320 mg). Operating characteristics for this BLRM design are described in [Appendix D](#).

During dose expansion, Amgen will conduct evaluations of the ongoing grade 4 or higher adverse event rate to assess if the threshold for early trial termination has been reached. The stopping rules use a Bayesian approach proposed by [Thall, et al \(1995\)](#) to terminate

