#### **10.6.2 Primary Endpoints**

##### **Safety Endpoints:**

Unless otherwise specified, statistical analyses on safety endpoints will be done using subjects from the safety analysis set, which includes subjects that are enrolled and received at least 1 dose of AMG 397.

Subject incidence of DLTs will be used to fit the BLRM model to estimate the probability of having a DLT across dose levels.

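### In Protocol Section 6.4 the AML non-hematologic DLT list has no attribution limit, so an unrelated Grade 3 or higher event counts as a Group 1B DLT

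*Protocol*

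**What the plan says.** Protocol Section 6.4 defines DLTs in three blocks.

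- **MM and NHL.** The lead sentence reads "A DLT is defined as a treatment-related AE(s), that occur during the DLT-observation period". The same list counts "Any grade 5 AE that is not clearly due to disease progression".
- **AML.** For blood counts, "Due to the nature of AML, hematologic adverse events will not be considered DLTs", except pancytopenia with a hypocellular, leukemia-free marrow lasting more than 42 days. The non-hematologic list then has four criteria: Grade 3 or higher nausea, vomiting or diarrhea beyond 3 days; Grade 3 or higher fatigue beyond 7 days; any other "Grade 3 adverse event" or worse; and a fourth that begins "Failure to recover from AMG 397 related toxicities to grade" and concerns recovery after a cycle delay of up to 14 days. Only the fourth names the drug.
- **All subjects.** Clinical tumor lysis syndrome and Hy's Law cases are added. No general rule on attribution or progression is given.

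Protocol Section 9.1.1 defines an adverse event without requiring a causal link to treatment. SAP Section 5 leaves DLT classification to the investigator under the protocol definition. Protocol Section 10.6.2 states that "Subject incidence of DLTs will be used to fit the BLRM model", and Section 10.4 that "The MTD target Toxicity Probability Interval (TPI) for DLT is (0.20, 0.33", with the upper limit included.

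**The concern.** A DLT rate is meant to measure what the drug does at a dose. If the AML list also admits events with another cause, the Group 1B rate is the drug rate plus a background. The same unrelated event would count in Group 1B and not in Group 1A.

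The protocol attaches four consequences to such an event:

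- It is fitted in the BLRM (Section 10.6.2), and Section 6.2.1.2 has late DLTs considered as well.
- If it falls in the observation period, it makes the subject DLT-evaluable (Section 6.2.1.2). Stopping for a non-DLT reason in that period would instead allow replacement (Section 3.4).
- It requires permanent discontinuation unless the subject is responding or may be responding (Section 6.2.1.3).
- It bars intra-subject escalation (Section 3.1).

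The direction is toward too low a dose. At stake is the AML MTD, a primary objective, rather than subject protection. Investigators who take the word toxicity to mean drug-caused would apply a different rule from those who follow the bullet literally, so sites could also differ.

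**Working it through.** **Step 1: the two lists side by side (Protocol Section 6.4).**

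| Element | MM and NHL | AML, non-hematologic |
|---|---|---|
| Limited to treatment-related events | Yes, in the lead sentence | Only in the failure-to-recover criterion |
| Death clearly due to progression left out | Yes | Not stated |
| Catch-all for other Grade 3 or higher events | Within the treatment-related limit | No attribution limit |

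Neither the all-subjects block nor SAP Section 5 fills the gap.

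**Step 2: which events are exposed.** These are not:

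- hematologic events, which the AML block excludes apart from the 42-day criterion;
- gastrointestinal events of 3 days or less and fatigue of 7 days or less, through the duration limits;
- expected worsening of the disease, which Section 9.1.1 does not treat as an adverse event.

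A realistic exposed event is a Grade 3 infection arising from neutropenia that the leukemia had already caused. The entry minimums for neutrophils, hemoglobin and platelets (Section 4.1, criterion 107) apply to MM and NHL only, and Section 6.6.1 describes neutropenic subjects as being at high risk of infectious complications.

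**Step 3: reproduce the plan's own figure.** Section 10.3 gives a 27% to 70% chance of at least one DLT among 3 subjects at true rates of 10% to 33%. The formula is 1 − (1 − p)³.

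- p = 0.10: 1 − 0.90³ = 0.271
- p = 0.33: 1 − 0.67³ = 0.699

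Both agree. That figure is not in dispute; the question is what the DLT rate contains.

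**Step 4: add unrelated events.** Let p be the drug DLT rate and u the probability of a qualifying unrelated event. The documents do not give u, so it is an assumption, shown over a range. With independence the counted rate is q = 1 − (1 − p)(1 − u).

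| u | q when p = 0.10 | P(at least 1 of 3) when p = 0.10 | q when p = 0.25 |
|---|---|---|---|
| 0 | 0.100 | 27.1% | 0.250 |
| 5% | 0.145 | 37.5% | 0.288 |
| 10% | 0.190 | 46.9% | 0.325 |
| 20% | 0.280 | 62.7% | 0.400 |
| 30% | 0.370 | 75.0% | 0.475 |

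**Step 5: when a dose in the target interval appears excessive.** Setting q = 0.33 gives u = 1 − 0.67/(1 − p).

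- p = 0.21: 1 − 0.67/0.79 = 15.2%
- p = 0.25: 1 − 0.67/0.75 = 10.7%
- p = 0.30: 1 − 0.67/0.70 = 4.3%

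These thresholds need no prior and no simulation.

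**The case against.** The strongest reply is that the list stands under headings that speak of toxicity, that investigators make the DLT call, and that many would apply relatedness without being told. That may well happen, but no text requires it. The list itself adds attribution to the word toxicities in its last criterion, so the word alone does not clearly carry it.

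A second reply is that the practical effect is small, and much of this stands. The BLRM only guides the dose level review team, which sees all available data (Section 6.2.1.2). Adverse events are also tabulated by relationship (Section 10.6.2). The team could discount an unrelated event, although no rule tells it to. Eligibility narrows the exposed set: ECOG 2 or better, life expectancy above 3 months, and no recent uncontrolled infection needing intravenous treatment. Part 1 is closed with 12 subjects in Part 1B (SAP Section 3.2), after a hold for troponin elevations (SAP Section 3.1).

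Three stronger readings are tempting, and the documents do not support them:

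- **Any severe event caused by the leukemia is a DLT.** Section 9.1.1 and the exclusions in the AML block remove many of these.
- **The re-challenge list in Section 6.2.1.3 shows that DLT criteria do not include relatedness**, because it says "Any treatment-related adverse event meeting DLT-criteria that recurs". The lead-in to that list already restricts it to events related to AMG 397. The repetition is therefore redundant and says nothing about the AML definition.
- **The loss in correct dose selection can be quantified.** That would need u and a fully specified prior. The documents give no u, and Section 10.4 does not state the prior correlation.

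**Conclusion.** The concern holds in a limited form. Applied literally, Section 6.4 makes a non-hematologic Grade 3 or higher adverse event unrelated to AMG 397 a Group 1B DLT, and that biases the AML MTD downward. The size depends on u. Under independence, u above 10.7% takes a dose with a drug DLT rate of 0.25 out of the target interval, and u above 4.3% does so at 0.30.

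The textual finding is firm; the size is conditional on u and independence. A reader might infer that the AML dose findings of Part 1 were in fact distorted, or that the later AML parts share the defect. Neither can be said. No unrelated event is documented as having been counted. The SAP follows protocol amendment 4, whose DLT text is not among the documents.

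Severity is minor to should-fix: the bias is conservative, the review team has discretion, and Part 1 is closed.

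**What to change.** In Section 6.4, change the third AML non-hematologic bullet to: *Any other Grade 3 or higher non-hematologic adverse event, unless clearly due to disease progression or clearly unrelated to AMG 397.* Apply the same qualifier to the gastrointestinal and fatigue bullets and to Grade 5 events. Leave the 42-day myelosuppression and 14-day delay criteria as they are.

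This is preferable to moving the MM and NHL lead sentence above all the lists. That sentence would bring in the DLT-observation period (at minimum 28 days), which conflicts with a criterion that needs more than 42 days. The proposed wording also keeps events of uncertain cause as DLTs, which suits a first-in-human trial.

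Check the DLT text for the later AML parts and make the same change there if the wording persists.

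The cost is a short qualifier in a few bullets. No visit, procedure or data item is added, because Section 9.2.1.1 already has the investigator record relatedness.

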**For all subjects:**

- Any Clinical TLS (refer to [Appendix K](#))

If a DLT of TLS is observed during the lead-in period, it will be attributed to the lead-in period and a modification may be made to the lead-in period regimen for subsequent cohorts. Any other DLTs observed during the lead-in and/or designated cohort dosing period may require a modification of the designated cohort dose (and/or lead-in period regimen, if appropriate) as directed per the Dose Escalation Guidelines.

Any subject meeting the criteria for Hy's Law case (ie, severe drug-induced liver injury) will be considered a DLT. A Hy's Law case is defined as: AST or ALT values of  $\geq 3x$  ULN AND with serum total bilirubin level (TBL) of  $> 2x$  ULN without signs of cholestasis and with no other clear alternative reason to explain the observed liver-related laboratory abnormalities (see [Section 6.7](#) for hepatotoxicity management and [Appendix A](#) for further explanation of Hy's law case and Management of Hepatic Function). Grade 3 or 4 elevation of serum lipase without clinical signs or symptoms of pancreatitis.

## **6.5 Potential Risk Management Guidelines for AMG 397**

### **6.5.1 Gastrointestinal Toxicity**

Evidence of gastrointestinal toxicity will be monitored in the FIH study through clinical evaluations, safety laboratory tests, stopping rules, and associated adverse events.

Management should be tailored to the appropriate treatment according to the local standard of care and institutional guidelines.

### **6.5.2 Bone Marrow Toxicity**

Monitoring of vital signs, hematology parameters and associated adverse events will be conducted in the FIH study. Specific eligibility criteria, stopping rules and dose-hold rules, pertaining to hematology parameters, are provided in [Section 6.2.1.3](#).

### **6.5.3 Reproductive Toxicity- Male**

Men of reproductive potential who are unwilling to practice an acceptable method of effective birth control will be excluded from the study. See [section 4.2](#) for list of acceptable methods of effective birth control.

### **6.5.4 Drug-drug interactions**

A list of prohibited drugs as well as subject exclusion criteria are included in the protocol. Subjects receiving any of the drugs cited in the exclusion criteria and/or prohibited drugs as listed in the FIH protocol will be excluded from this study. Caution should be exercised when administering AMG 397 with drugs that have a narrow therapeutic window and prescribing information that includes contraindications, warnings or precautions related to their use with known inhibitors of CYP34A and P-gp.

### **6.5.5 Hepatobiliary Toxicity**

Evidence of hepatobiliary toxicity will be monitored as outlined in the study protocol through clinical evaluations, safety laboratory tests, stopping rules, and associated adverse events.

### 6.5.6 Cardiovascular Toxicity

Adverse events associated with cardiac function will be monitored through blood pressure, heart rate, echocardiogram, and ECG measurements. Subsequent withholding rules, as outlined in the study protocol, will be followed.

### 6.5.7 Tumor Lysis Syndrome (TLS)

#### Prophylaxis and Management of TLS

Tumor lysis syndrome prophylaxis must be initiated in all subjects prior to the first dose of AMG 397 and prior to every dose escalation.

The management recommendations below focus on the minimum initial responses required. If a diagnosis of TLS is established, ongoing intensive monitoring and multi-disciplinary management will be conducted per institutional protocols (Coiffier et al, 2008; Cairo et al, 2004).

- Initiate allopurinol or equivalent to reduce uric acid level. This should be initiated at least 72 hours prior to dosing. Treatment may need to be continued for up to 5 weeks. Other agents to reduce uric acid level, such as rasburicase may be used per PI discretion. Dosing per institutional guidelines.
- All subjects will be hospitalized for intensive monitoring:
  - For the first 2 doses received, beginning 24 hours prior to first dosing day (Day -1) until 24 hours post the second dose
  - Once lead-in dosing is initiated (see [Section 6.2.1.1.1](#)):
    - For the first 2 doses received (Lead-in dosing), beginning at least 24 hours prior to first dosing day (Day -1) until 24 hours post the second dose
    - Each time an additional week of lead-in dosing is instituted ([Section 6.2.1.1.1](#))
    - For the first 2 doses received after the dose is escalated (target dose) beginning at least 24 hours prior to dosing day (usually day 7) until 24 hours post the second dose
- During hospitalization, intensive safety laboratory monitoring per designated timepoints per [Table 4](#) and/or [Table 5](#) to identify and prompt management of any metabolic changes.
  - Pre-treatment serum chemistry and hematology laboratory samples must be drawn within 24 hours prior to first dose, and electrolyte values (ie, potassium, uric acid, inorganic phosphorus, calcium) must be reviewed and within normal range prior to AMG 397 dosing. The investigator's decision to proceed with AMG 397 treatment initiation may be based on these laboratory values. These labs must be reviewed in real time by the investigator.

**NOTE:** If the potassium, uric acid, inorganic phosphate and/or creatinine values are higher than the normal range or the calcium is lower or higher than the normal range, dosing can be resumed following review of

laboratory values and agreement between the Amgen medical monitor and investigator.

- Prophylactic reductions of potassium, inorganic phosphorus and/or uric acid above of normal range prior to dosing are recommended per PI discretion.
- Day 2 dosing of AMG 397 should not be administered until the 24 hours post-dose laboratory values are reviewed by the investigator.
- All 24-hour laboratory assessments may be taken  $\pm$  2 hours, if necessary.
- Within the first 24 hours after either the first dose or dose escalation, if any laboratory criteria ([Appendix L](#)) are met, no additional AMG 397 doses should be administered until resolution. A rapidly rising serum potassium is a medical emergency.
- Upon admission, IV fluids (eg, D5 1/2 normal saline) should be initiated at a rate of at least 1 mL/kg/hr rounded to the nearest 10 mL (target 150 to 200 mL/hr; not < 50 mL/hr). Modification of fluid rate should also be considered for individuals with specific medical needs and as needed per Investigator discretion.
- Monitor for signs and symptoms of TLS (eg, fever, chills, tachycardia, nausea, vomiting, diarrhea, diaphoresis, hypotension, muscle aches, weakness, paresthesias, mental status changes, confusion and seizures). If any clinical features are observed, recheck potassium, phosphorus, uric acid, calcium and creatinine within 1 hour.
- Nephrology (or other acute dialysis service) consultation should be considered upon admission per institutional standards at investigators' discretion to ensure emergency dialysis is available and the appropriate staff is aware and prepared.
- Management recommendations of laboratory abnormalities as stated below:

Approved

Abnormality	Management Recommendations 
Hyperkalemia (including rapidly rising potassium)	
Potassium $\geq 0.5$ mmol/L increase from prior value (even if potassium within normal limits [WNL])	
 
• Recheck potassium, phosphorus, uric acid, calcium and creatinine in 1 hour STAT. If further <math>\geq 0.2</math> mmol/L increase in potassium, but still <math><</math> upper limit of normal (ULN), manage as per potassium <math>\geq</math> ULN. Otherwise recheck in 1 hour.
 
• Resume per protocol testing if change in potassium is <math>< 0.2</math> mmol/L, and potassium <math><</math> ULN, and no other evidence of tumor lysis.
 
• At discretion of Investigator, may recheck prior to hospitalization. If stable or decreased, and still WNL, hospitalization is at the discretion of the Investigator. Potassium, phosphorus, uric acid, calcium and creatinine must be rechecked within 24 hours.
 

Potassium $>$ upper limit of normal	
 
• Perform STAT ECG and commence telemetry.
 
• Nephrology notification with consideration of initiating dialysis.
 
• Administer Kayexalate 60 g (or Resonium A 60 g).
 
• Administer furosemide 20 mg IV <math>\times</math> 1.
 
• Administer calcium gluconate 100 – 200 mg/kg IV slowly if there is ECG/telemetry evidence of life-threatening arrhythmias.
 
• Recheck potassium, phosphorus, uric acid, calcium and creatinine in 1 hour STAT.               
 
○ If potassium <math><</math> ULN 1 hour later, repeat potassium, phosphorus, uric acid, calcium and creatinine 1, 2 and 4 hours, if no other evidence of tumor lysis.
 
 
 

Approved

Abnormality	Management Recommendations 
Hyperkalemia (including rapidly rising potassium) (continued)	
Potassium $\geq$ 6.0 mmol/L (6.0 mEq/L) and/or symptomatic (e.g., muscle cramps, weakness, paresthesias, nausea, vomiting, diarrhea)	
 
• Perform STAT ECG and commence telemetry.
 
• Nephrology (or other acute dialysis service) assessment with consideration of initiating dialysis.
 
• Administer Kayexalate 60 g (or Resonium A 60 g).
 
• Administer furosemide 20 mg IV <math>\times</math> 1.
 
• Administer insulin 0.1 U/kg IV + D25 2 mL/kg IV.
 
• Administer sodium bicarbonate 1 to 2 mEq/kg IV push.               
 
○ If sodium bicarbonate is used, rasburicase should not be used as this may exacerbate calcium phosphate precipitation.
 
 
 
• Administer calcium gluconate 100 to 200 mg/kg IV slowly if there is ECG/telemetry evidence of life-threatening arrhythmias. Do not administer in same IV line as sodium bicarbonate.
 
• Recheck potassium, phosphorus, uric acid, calcium and creatinine every hour STAT.
 

Hyperuricemia	
Uric acid $\geq$ 8.0 mg/dL (476 $\mu$ mol/L)	
 
• Consider rasburicase (0.2 mg/kg as an intravenous infusion over 30 minutes).               
 
○ If rasburicase is used, sodium bicarbonate should not be used as this may exacerbate calcium phosphate precipitation.
 
 
 
• Recheck potassium, phosphorus, uric acid, calcium and creatinine in 1 hour STAT.
 

Uric acid $\geq$ 10 mg/dL (595 $\mu$ mol/L)  OR  Uric acid $\geq$ 8.0 mg/dL (476 $\mu$ mol/L) with 25% increase and creatinine increase $\geq$ 0.3 mg/dL ( $\geq$ 0.027 mmol/L) from pre-dose level	
 
• Administer rasburicase (0.2 mg/kg as an intravenous infusion over 30 minutes).               
 
○ When rasburicase is used, sodium bicarbonate should not be used as this may exacerbate calcium phosphate precipitation.
 
 
 
• Consult nephrology (or other acute dialysis service).
 
• Recheck potassium, phosphorus, uric acid, calcium and creatinine in 1 hour STAT.
 
• If uric acid <math><</math> 8.0 mg/dL 1 hour later, repeat potassium, phosphorus, uric acid, calcium and creatinine 2 and 4 hours later, if no other evidence of tumor lysis.
 

Approved

Abnormality	Management Recommendations 
Hypocalcemia	
Calcium $\leq$ 7.0 mg/dL (1.75 mmol/L) AND Patient symptomatic (e.g., muscle cramps, hypotension, tetany, cardiac arrhythmias)	
 
Administer calcium gluconate 50 to 100 mg/kg IV slowly with ECG monitoring.
 
Telemetry.
 
Recheck potassium, phosphorus, uric acid, calcium and creatinine in 1 hour STAT.
 
If calcium normalized 1 hour later, repeat potassium, phosphorus, uric acid, calcium and creatinine 2 and 4 hours later, if no other evidence of tumor lysis.
 
Calculate corrected calcium and check ionized calcium if albumin low.
 

Hyperphosphatemia	
Phosphorus $\geq$ 5.0 mg/dL (1.615 mmol/L) with $\geq$ 0.5 mg/dL (0.16 mmol/L) increase	
 
Administer a phosphate binder (e.g., aluminum hydroxide, calcium carbonate, sevelamer hydroxide, or lanthanum carbonate).
 
Nephrology (or other acute dialysis service) notification (dialysis required for phosphorus <math>\geq</math> 10 mg/dL).
 
Recheck potassium, phosphorus, uric acid, calcium and creatinine in 1 hour STAT.
 
If phosphorus <math><</math> 5.0 mg/dL 1 hour later, repeat potassium, phosphorus, uric acid, calcium and creatinine 2 and 4 hours later, if no other evidence of tumor lysis.
 

Creatinine	
Increase $\geq$ 25% from baseline	
 
Start or increase rate of IV fluids.
 
Recheck potassium, phosphorus, uric acid, calcium and creatinine in 1 to 2 hours STAT.
 

Approved

## 6.6 Support Care Guidelines for AMG 397

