### Appendix L. Cairo-Bishop Definition of Laboratory Tumor Lysis Syndrome

Element	Value		Change from Baseline
Uric Acid	$\geq 476 \mu\text{mol/L}$ (8 mg/dL)	-OR-	25% increase from baseline
Potassium	$\geq 6.0 \text{ mmol/L}$ (6 mg/L)	-OR-	25% increase from baseline
Inorganic phosphorus	$\geq 1.45 \text{ mmol/L}$ (4.5 mg/dL)	-OR-	25% increase from baseline
Calcium	$\leq 1.75 \text{ mmol/L}$ (7.0 mg/dL)	-OR-	25% decrease from baseline

Note: Two or more elements with laboratory values out of range or changes from baseline.

Approved

## Amendment 1

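### In the Section 6.5.7 TLS table, the upper potassium row and the upper uric acid row each order a drug that the other row excludes, and nothing says which yields

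*Protocol*

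**What the plan says.** Protocol Section 6.5.7 introduces its table with this sentence: "The management recommendations below focus on the minimum initial responses required". Once TLS is diagnosed, it leaves ongoing monitoring and management to institutional protocols.

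- **Upper potassium row.** The trigger is potassium at or above "6.0 mmol/L (6.0 mEq/L) and/or symptomatic". Among the actions is "Administer sodium bicarbonate 1 to 2 mEq/kg IV push", followed by the note "If sodium bicarbonate is used, rasburicase should not be used as this may exacerbate calcium phosphate precipitation".
- **Upper uric acid row.** The trigger is uric acid of at least 10 mg/dL, or at least 8.0 mg/dL "with 25% increase and creatinine increase" of at least 0.3 mg/dL. The row orders rasburicase and notes: "When rasburicase is used, sodium bicarbonate should not be used as this may exacerbate calcium phosphate precipitation".

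Neither order depends on the other analyte. Under prophylaxis, the same section also says: "Other agents to reduce uric acid level, such as rasburicase may be used per PI discretion".

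**The concern.** Each of the two rows contains a drug order and an exclusion of the drug that the other row orders. Potassium and uric acid are both elements of laboratory TLS in Appendix L, so a subject may meet both triggers. The investigator would then have two instructions that cannot both be carried out, in an acute setting with STAT rechecks at hourly intervals and no rule of precedence. The table exists to give sites a defined initial response, and for this combination it does not give one. TLS is a recognised hazard here: the Risk Assessment part of Section 2.2.4 reports clinical TLS with a drug of the same mechanism.

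**Working it through.** No statistical figure is involved. The check compares the rows of the table and then looks for a precedence rule.

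**Step 1: the two upper rows together.** Write B for bicarbonate given and R for rasburicase given.

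- Upper potassium row: B; and if B, then not R.
- Upper uric acid row: R; and if R, then not B.
- Both rows apply: B and R are both required, while B requires not R and R requires not B. No course of action satisfies all four statements.

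**Step 2: every pair of potassium and uric acid rows.** The table has three potassium rows and two uric acid rows, so 3 × 2 = 6 pairs.

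| Potassium row | Uric acid ≥8.0 mg/dL only (rasburicase to be considered) | Uric acid ≥10 mg/dL, or ≥8.0 mg/dL with the 25% and creatinine criteria (rasburicase ordered) |
|---|---|---|
| Rise of ≥0.5 mmol/L from prior value | No bicarbonate listed; no conflict | No bicarbonate listed; no conflict |
| Above the upper limit of normal | No bicarbonate listed; no conflict | No bicarbonate listed; no conflict |
| ≥6.0 mmol/L and/or symptomatic | Bicarbonate ordered, rasburicase optional; both rows can be followed by not using rasburicase | **Both drugs ordered, each excludes the other** |

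One pair of six is a direct contradiction.

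**Step 3: what remains executable in that pair.** The ECG and telemetry, Kayexalate or Resonium A, furosemide, insulin with D25, calcium gluconate under its stated ECG condition, the nephrology or dialysis input and the repeat laboratory tests are unaffected. Only the two drug orders collide.

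**Step 4: search for a precedence rule.** There is none in the remaining text or rows of Section 6.5.7, in Appendix K (clinical TLS grading) or in Appendix L (laboratory TLS definition). The SAP is silent on the point.

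**The case against.** The best defence is that the table offers recommendations. Its column is headed that way, the exclusions are worded with should, and the potassium note opens with an if, so the paired notes could be read as marking alternatives. Institutional protocols and nephrology or dialysis input are also in play. Part of this stands: it would be wrong to call the orders mandatory or to say sites are left without direction. It does not remove the conflict. The section presents these as minimum initial responses, the two drug lines carry no condition on the other analyte, and institutional protocols are invoked only for ongoing management after a TLS diagnosis. Recommendations can contradict each other too, and even if the drugs were meant as alternatives, the table does not say how to choose.

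A reader might also infer more than the documents support:

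- **That any subject with high potassium and high uric acid cannot be managed.** Five of the six row pairs are compatible, and most actions in the sixth can proceed.
- **That the two triggers are expected together.** Appendix L requires "Two or more elements with laboratory values out of range or changes from baseline". Potassium with uric acid is one of six possible pairs among its four elements (4 × 3 / 2 = 6), and a 25% change from baseline can qualify on its own. Its absolute uric acid value of 8 mg/dL matches the row where rasburicase is optional, not the 10 mg/dL row.
- **That rasburicase given earlier as prophylaxis creates a second contradiction.** The bicarbonate exclusion sits inside the uric acid rows. No text extends it to earlier prophylactic use, and no look-back period is given. This is an ambiguity worth clearing up, not a demonstrated conflict.
- **That dose-limiting toxicity (DLT) assessment is compromised.** Under Section 6.4, the occurrence of clinical TLS makes the DLT, not the treatment chosen. No effect on DLT classification or on the dose-escalation model is shown.

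**Conclusion.** The concern holds for one pair of rows. When potassium is at least 6.0 mmol/L and/or the subject is symptomatic, and uric acid is at least 10 mg/dL (or meets the 8.0 mg/dL composite), the table's two drug orders contradict each other and no precedence is stated. The text is wrong as written and should be corrected because it governs an acute safety response. No frequency can be attached, since the documents give neither a TLS rate nor a joint rate for the two triggers.

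The conclusion assumes that the supplied protocol text is the one in force. That protocol carries amendment 1, while SAP Section 1 refers to protocol amendment 4, and the later protocol is not available here. If a later amendment already resolves the two rows, the point falls away. This review takes no position on which drug or rule is right.

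**What to change.** Reconcile the upper potassium row and the upper uric acid row in the Section 6.5.7 table, so that it states what applies when both triggers are met. In the same edit, state whether the exclusion covers rasburicase already given, including as prophylaxis, and over what period. The sponsor's medical team must decide the content; none is proposed here. First check whether amendments 2 to 4 have already done this.

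The cost is a single table edit in a protocol amendment. It needs no new procedure, assessment or data.
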